8.4. Statistical/Analytical Methods

The statistical analyses will be performed by a Contract Research Organisation (CRO), managed by the Sponsor's Head of Biostatistics and the Commercialised Products Data Management.

A statistical analysis plan (SAP) will be prepared as a separate document to fully describe the planned statistical analysis, including table templates, figures and printouts (TFP).

Statistical evaluation will be performed with the assistance of the Statistical Analysis System (SAS)[®] (version 8 or higher).

9.4.1. Selection of the Centres and Selection of Patients

Summarised descriptive statistics will be provided (n, mean, standard deviation [SD], median, minimum, maximum) or else frequency counts of the data collected

in the course of the centre selection process (characteristics of all pre-selected services gathered through a pre-selection visit: geographical location, type of service -Urology or Radiation Therapy-, number of patients treated yearly with LHRH analogues, in order to be able to categorise the services over the base of their size) with the aim of documenting the suitability of the selected centres (and also the reasons for not participating).

Summarised descriptive statistics will be provided (n, mean, standard deviation [SD], median, minimum, maximum) or else frequency counts of the data collected in the patients' screening record (key characteristics of the screened patients population: year of birth, sex, year in which prostate cancer was diagnosed and, in the case of not-included patients, the reason of not inclusion) with the aim of documenting the suitability of the selected patients (and also the reasons for not having selected the remaining ones).

Each service may include 10-12 patients (which is a mean over the base of the number of active services). Since ours is a competitive clinical study, a service could include a greater number of patients with a maximum 30 subjects.

9.4.2. Demographic and Other Characteristics at Baseline

Summarised descriptive statistics will be provided (n, mean, standard deviation [SD], median, minimum, maximum) or else frequency counts of the demographic and baseline data regarding the total populations included / treated.

9.4.3. Final Destination of Subjects and Withdrawals

Numbers and percentages of the subjects recruited and included in each population will be tabulated by centres. The reasons for excluding subjects from each of the populations will also be tabulated. Additionally, the numbers of subjects treated, subjects who discontinued their medication and subjects who

completed the study will be tabulated. A table showing the main reasons for discontinuation of the study drug will also be prepared.

9.4.4. Evaluation of Efficacy

As stated in section 8.1., the primary variable will be the prevalence of the Metabolic Syndrome according to the ATP III Panel definition, i.e. the presence of three or more risk factors, as shown by the table below:

Table II.6-1. Clinical Identification of the Metabolic Syndrome *

Risk Factor	Level of Definition
Abdominal obesity	Abdominal perimeter [†] > 102 cm
Triglycerides	≥ 150 mg/dl
HDL-cholesterol	< 40 mg/dl
Blood pressure	≥ 130/85 mmHg
Fasting glucose	≥ 110 mg/dl

* The ATP III Panel found no suitable evidence for recommending that the usual insulin-resistance determination (e.g. plasma insulin), the proinflammatory status (e.g. high-sensitivity C-reactive protein) or prothrombotic status (e.g. fibrinogen or PAI-1) be performed for diagnosing the metabolic syndrome.

[†] Some men may have many metabolic risk factors even when their abdominal perimeter is just slightly enlarged, e.g. 94 – 102 cm. The resistance to insulin in those persons may have a strong genetic component. A change of habits may be beneficial to them and also to those men with a far more enlarged abdominal perimeter.

The difference between Metabolic Syndrome at baseline and at study completion will be calculated, and also the 90% confidence interval associated to it in accordance with paired data. Newcombe's method 10, 1998c, will be used with this purpose. If the CI's upper limit were lower than 5%, it may be concluded that a clinically not significantly increased prevalence of SM was found in the study.

The secondary parameters are: BMI, Blood pressure, Weight and Abdominal perimeter.

Regarding secondary parameters, statistics will only be issued including confidence intervals based on the raw data from every evaluation; the analyses will be stratified as per the status of the Metabolic Syndrome.

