5.2. Secondary Objectives

Modifications of the parameters below at the baseline visit, at 6 months and at 12 months will be assessed as secondary objectives:

- Physical exploration:
 - i. BMI
 - ii. Blood pressure
 - iii. Weight
 - iv. Abdomen perimeter

- Laboratory tests:
 - i. HbA1c
 - ii. Haemoglobin
 - iii. Triglycerides

- iv. Total, LDL and HDL cholesterol
- v. PSA
- vi. Total testosterone
- vii. Glycaemia
- viii. C-Reactive Protein

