8.2. Definitions of Analysis Populations

Included and treated population:	All treated subjects
Complete population:	All treated subjects paying the Month 12 end visit

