9.2.1. Analysis Populations

The primary analysis will be performed on the whole of the population, Additionally, the analysis will be repeated on the included and treated population.

Analysis of the safety data will be performed on the treated population.

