8.3. Sample Size Determination

If we assume:

- 1) metabolic syndrome (MS) prevalence = 30% at study initiation,
- 2) that such prevalence will increase by 2% along the study,
- 3) that 5% of prevalence increase is clinically not significant,
- 4) that $\alpha = 5\%$ (unilateral) and power = 80%, and that we mean to demonstrate that the increase of MS prevalence will be lower than 5% (non-inferiority study)

Using 500 subjects, the upper limit of the unilateral confidence interval (CI) observed of 95% will be expected to be lower than 0.050 with a power of 80% when the expected difference, $p_T - p_S$, D_1 , is 0.020 and the proportion of discordants, $h = p_{10} + p_{01}$, is 0.070, and the proportion yes in both cases, p_{11} , is 0.290. The results are based on 5000 simulations that used the Newcombe-Wilson's score method to produce the confidence interval (Newcombe RG (1988): *Improved confidence intervals for the difference between binomial proportions based on paired data*. *Statistics in Medicine* 17:2635-2650).

Considering a 10% dropout rate, the final sample size is $500/0.9 = 556$ subjects. The recruitment of 556 subjects from some 60 Spanish centres has been devised. Each of the centres will be requested to enlist them following a chronological order based on the date of the first visit carried out at the centre.

Assuming this sample size, the MS prevalence will be estimated with a precision of 0.038 (for a 5% bilateral alpha).

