9.4.5. Evaluation of Safety

All the safety data will be included in the subjects' data lists. Tabulated analyses and summaries will be based on the general population.

As this is a non-interventional study, only treatment-related Adverse Events (AEs) will be recorded. The AEs will be classified according to the Medical Dictionary for Regulatory Activities (MedDRA), using the term and the organic system class preferred by MedDRA. The AE lists shall be submitted by subject, organic system class and preferred term.

The incidence of all treatment-related emergent AEs (TRAEs) and all SAEs reported will be tabulated. Additionally, tabulated summaries according to maximum severity, relationship with the drug and also AEs/TRAEs associated with early withdrawal of the study medication will be submitted.

TRAE is defined as any AE occurring during the active phase of the study, provided that:

- it had not occurred before receiving the first dose of study drug, or
- it had occurred before receiving the first dose of the study drug but its severity increased in the course of the active phase of the study, or
- it had occurred before receiving the first dose of the study drug, its severity was the same but its relationship to the study drug was established in the course of the active phase of the study.

Treatment-related emergent AEs shall be marked with (*) in the lists of AEs.

Concomitant medication will be coded according to the WHO Drug Dictionary, and summarised including the number and percentage of subjects receiving concomitant medication as <drug class and preferred drug name>.

The statistical summary (mean, median, SD and interval, if applicable) will be displayed by treatment group and also overall regarding heart rate determination and laboratory tests at each assessment, and the changes occurred from baseline will be highlighted. As to the analytical data (including Fasting glucose, HbA1c, Haemoglobin, Triglycerides, Total cholesterol, LDL-cholesterol, HDL-cholesterol, Thyroid hormones (TSH), PSA, Total testosterone, C-Reactive protein), the data printouts will point out at the abnormal values, with a list of those that may be significantly abnormal. Time-progress tables of the amount and percentage of subjects with low, normal or high values or with either normal or abnormal exams will be displayed.

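### For BMI, blood pressure, weight and abdominal perimeter, Protocol 9.4.4 allows only visit-by-visit raw intervals, so the change from baseline set as the objective in 5.2 gets no confidence interval

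*Protocol*

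**What the plan says.** Protocol 5.2 states the secondary objective: "Modifications of the parameters below at the baseline visit, at 6 months and at 12 months will be assessed as secondary objectives". It lists four physical items and eight laboratory headings.

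Protocol 9.4.4 narrows the list: "The secondary parameters are: BMI, Blood pressure, Weight and Abdominal perimeter". For these it says that "statistics will only be issued including confidence intervals based on the raw data from every evaluation", stratified by metabolic syndrome status.

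Protocol 9.4.5 deals with the laboratory tests under safety. It plans a statistical summary "regarding heart rate determination and laboratory tests at each assessment, and the changes occurred from baseline will be highlighted", together with tables over time of low, normal and high values. No confidence interval for the change is mentioned.

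The section on analysis of subgroups adds descriptive statistics overall and by metabolic syndrome status at entry, and does not mention change.

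The section defining the analysis populations has an included and treated population (all treated subjects) and a complete population: "All treated subjects paying the Month 12 end visit". Section 9.2.1 assigns populations to the primary and the safety analyses. It names none for the secondary parameters.

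**The concern.** The objective is about change and the planned statistic is about level. A raw interval at one visit carries the full between-patient variance, most of which cancels when each man is compared with himself. A reader given three separate visit intervals for weight or waist gets no measure of uncertainty for the change, and can easily misjudge it by comparing intervals that were not built for that purpose.

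The wording matters because it is restrictive. A protocol may leave change-from-baseline tables to the SAP, but the word *only* rules them out. A SAP that follows the sentence omits the change, and a SAP that adds it departs from the protocol. The restriction is also out of line with the rest of the plan. The primary endpoint is analysed as paired data in the same section, and the laboratory values have changes from baseline. Abdominal perimeter and blood pressure, both components of the metabolic syndrome definition, do not.

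**Working it through.** **The plan's own figures.** The protocol gives no figure for the secondary analysis. Those for the primary endpoint, in the section on sample size determination, reproduce:
- Inputs: n = 500, difference 0.020, discordant proportion 0.070, both-yes proportion 0.290. Gains are (0.070 + 0.020)/2 = 0.045 and losses (0.070 − 0.020)/2 = 0.025. Simulating Newcombe's method 10 (200,000 runs, one-sided 95% upper limit below 0.05) gives power 0.801, or 0.812 without the continuity correction, against the stated 80%.
- 500/0.9 = 555.6, so 556.
- 1.96 × √(0.30 × 0.70/556) = 0.038.

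None of these depends on the secondary parameters.

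**Inputs for the check.** From the protocol: 556 recruited and 500 evaluable after 10% dropout. Assumed, because the protocol gives neither: the within-patient correlation r and the SD. Results are therefore in SD units over a range of r, for Month 12. The expected number at Month 6 is not stated.

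**95% half-width of the paired mean change**, 1.96 × √(2(1 − r)/500):

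| r | Half-width (SD) | Relative to 0.121 SD |
|---|---|---|
| 0.5 | 0.088 | 73% |
| 0.7 | 0.068 | 56% |
| 0.8 | 0.055 | 46% |
| 0.9 | 0.039 | 32% |

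**Half-width if the two visits are treated as independent**, 1.96 × √(1/556 + 1/500) = 0.121 SD. With the same 500 men at both visits it is 1.96 × √(2/500) = 0.124 SD, so the loss from ignoring the pairing does not need any dropout.

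**In units, for weight** (assumed SD 12 kg, r = 0.95):
- Baseline interval: 1.96 × 12/√556 = ±1.00 kg.
- Month 12 interval: 1.96 × 12/√500 = ±1.05 kg.
- Paired change: 1.96 × 12 × √(0.10/500) = ±0.33 kg.

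A mean gain of 1 kg would leave the two visit intervals overlapping, while the paired interval would exclude zero.

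**Changing membership**, relevant only if all treated men are analysed. The 56 of 556 who drop out leave the Month 12 mean. If they differ at baseline from the completers by d SD, the visit mean moves by (56/556) × d with no true change: 0.025 SD for d = 0.25, 0.05 SD for d = 0.5 and 0.10 SD for d = 1. The values of d are assumptions.

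**The case against.** The strongest reply is that 9.4.4 merely says the secondary parameters are descriptive. On this reading *only* follows the primary decision rule and means that no hypothesis test is made, and the SAP would supply change columns. This is possible, especially in a translated text, but it leaves the reference to raw data from every evaluation in place, and nothing else in the protocol plans a change for these four parameters.

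A second reply is that, in men with both values, the difference of the visit means equals the mean paired change, so the point estimate can be recovered. That is correct. What cannot be recovered from the visit summaries is its interval.

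Several stronger readings are tempting, and the protocol does not support them:
- A reader might infer that the secondary objective as a whole goes unestimated. It does not: for the laboratory tests 9.4.5 says that "the changes occurred from baseline will be highlighted".
- A reader might infer that the visits compare different sets of patients. This is a risk in the included and treated population. In the complete population, baseline and Month 12 hold essentially the same men, apart from missing items.
- A reader might infer that change will be judged by overlapping intervals or by an independent-samples comparison. The protocol plans neither. The 0.121 SD figure shows what is lost if someone does so.
- A reader might infer that the study's main result is weakened. The primary objective is the prevalence of metabolic syndrome, and it has a paired interval.

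**Conclusion.** The point stands for four parameters: BMI, blood pressure, weight and abdominal perimeter. The protocol sets their modification as an objective, then restricts the analysis to a form that gives no interval for it, and names no population for them. For the laboratory items the gap is smaller: change is planned, but no interval for it is stated.

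The mismatch rests on the text alone. Its size rests on assumptions. With 500 completers and r between 0.5 and 0.9, the paired interval is about 73% to 32% as wide as one that ignores the pairing. A dropout shift of about 0.05 SD needs both the included and treated population and a 0.5 SD baseline difference in the 10% lost. This is a matter that should be corrected. It does not touch the primary analysis, the 5% decision rule or the sample size of 556.

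**What to change.** In Protocol 9.4.4, delete *only* and replace the sentence on secondary parameters along these lines:

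> For each secondary parameter, the within-patient change from baseline to Month 6 and from baseline to Month 12 will be estimated as the mean paired difference with its 95% confidence interval, in subjects with both values. The analysis population is [to be named]. Raw summaries at each visit will be shown in addition.

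The sponsor should name one of the two defined populations and report the number of pairs at each time point. A repeated-measures model using all available visits is an option, not a requirement, in a descriptive study. The paired difference removes the shift caused by dropouts who differ at baseline, but it still describes only men with both values, and the report should say so. The same interval could be added to the laboratory changes in 9.4.5.

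The measurements are already scheduled at baseline, Month 6 and Month 12. The cost is the wording and a few more table columns, with no new data and no more patients.

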9.4.5. Evaluation of Safety

All the safety data will be included in the subjects' data lists. Tabulated analyses and summaries will be based on the general population.

As this is a non-interventional study, only treatment-related Adverse Events (AEs) will be recorded. The AEs will be classified according to the Medical Dictionary for Regulatory Activities (MedDRA), using the term and the organic system class preferred by MedDRA. The AE lists shall be submitted by subject, organic system class and preferred term.

The incidence of all treatment-related emergent AEs (TRAEs) and all SAEs reported will be tabulated. Additionally, tabulated summaries according to maximum severity, relationship with the drug and also AEs/TRAEs associated with early withdrawal of the study medication will be submitted.

TRAE is defined as any AE occurring during the active phase of the study, provided that:

- it had not occurred before receiving the first dose of study drug, or
- it had occurred before receiving the first dose of the study drug but its severity increased in the course of the active phase of the study, or
- it had occurred before receiving the first dose of the study drug, its severity was the same but its relationship to the study drug was established in the course of the active phase of the study.

Treatment-related emergent AEs shall be marked with (*) in the lists of AEs.

Concomitant medication will be coded according to the WHO Drug Dictionary, and summarised including the number and percentage of subjects receiving concomitant medication as <drug class and preferred drug name>.

The statistical summary (mean, median, SD and interval, if applicable) will be displayed by treatment group and also overall regarding heart rate determination and laboratory tests at each assessment, and the changes occurred from baseline will be highlighted. As to the analytical data (including Fasting glucose, HbA1c, Haemoglobin, Triglycerides, Total cholesterol, LDL-cholesterol, HDL-cholesterol, Thyroid hormones (TSH), PSA, Total testosterone, C-Reactive protein), the data printouts will point out at the abnormal values, with a list of those that may be significantly abnormal. Time-progress tables of the amount and percentage of subjects with low, normal or high values or with either normal or abnormal exams will be displayed.

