8.3. Adverse Event Recording

Any adverse events experienced by the patients in the course of the study will be recorded.

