8.4. Study Visits

8.4.1. Baseline Visit (Month 0)

The patients should be explained the programme in detail before entering the study. Additionally, the following will be obtained and recorded:

- Patients will be confirmed to satisfy all inclusion and exclusion criteria
- Patients will sign the informed consent
- Demographic variables: initials, date of birth, race
- Current clinical history: including the prostate cancer current stage and the treatments received up to the moment of entering the study
- Record of concomitant medications
- Record of concomitant diseases
- Physical examination: including systolic and diastolic blood pressure determination (all the investigators shall use the same model of sphygmomanometer), measurement of the abdominal perimeter (all the investigators shall use the same tape measure), and weight
- Analytical determinations: Glycaemia, HbA1c, Haemoglobin, Lipid profile: total cholesterol, HDL-cholesterol, LDL-cholesterol and triglycerides), Thyroid hormones (TSH), PSA, Total testosterone and C-Reactive protein
- Assessment of Metabolic Syndrome
- Record of the treatment with quarterly LHRH analogues
- Record of adverse events considered to be associated with the LHRH analogues, including local tolerability of the injection

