11.2 Procedure for Recording and Notifying Adverse Reactions

Every adverse reaction, independently of its severity and of its suspected relationship with the study drug, should be recorded in the relevant section of the Case Report Form.

The Investigator should let the Sponsor know any severe adverse reaction within a maximum 24 hours following his/her own awareness of same.

The Sponsor must report the suspected severe adverse reactions to the Competent Authorities within a maximum 15 calendar days from learning about the adverse reaction.

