11.2.1 Adverse Reactions Record

Adverse reaction: Any response to a drug that is harmful and unintended, and occurring at normally-administered doses to humans for prophylaxis, diagnosis or treatment of diseases, or for the restoration, correction or modification of physiological functions. The term also includes all harmful clinical consequences of the dependence, the abuse and the wrong use of drugs, including those consequences caused by drug use under conditions that are not those for which the medicine has been approved, and the ones caused by misadministration (RD 1344 / 2007).

Each investigator will be responsible for evaluating any adverse event (be it spontaneously reported by the patient or objectively detected following a medical questioning) occurring in the course of the study.

If, in the Investigator's opinion, there were or there could be a causal relationship with the study drug and consequently the adverse event were labelled as adverse reaction, the Investigator should state so in the specific form within the Case Report Form (CRF), and report:

- ⇒ date of onset,
- ⇒ length,
- ⇒ intensity: to be assessed with the following classification:

- Mild: an adverse reaction, generally transient, that does not interfere with the patient's normal daily activities.
- Moderate: an adverse reaction that limits the patient's ability to carry out normal daily activities, but does not prevent their performance.
- Severe: an adverse reaction whose unbearable discomfort or pain make carrying out normal daily activities impossible for the patient.

- ⇒ action taken by the doctor (e.g.: none, dose reduction, permanent discontinuation)
- ⇒ outcome (e.g.: death, restoration, improvement, sequels, unknown, etc.)
- ⇒ causality assessment: related, unrelated.

The Investigator should ask the patient “Have you experienced any discomfort since you have been administered the medication?” (or something similar) with the aim to facilitate reporting of potential adverse reactions by the patient.

11.2.2 Adverse Reactions Requiring Immediate Reporting:

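### Section 8.3 records any adverse event, section 9.4.5 records only treatment-related ones, and section 11.2 does not settle which rule applies

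*Protocol*

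**What the plan says.** Five places in the Protocol bear on which adverse events are recorded.

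- **Section 8.3 (Adverse Event Recording)** sets no causal condition: "Any adverse events experienced by the patients in the course of the study will be recorded".
- **Sections 8.4.1 and 8.4.2**, the item lists for baseline and for Months 6 and 12, ask for the same thing at each visit: "Record of adverse events considered to be associated with the LHRH analogues, including local tolerability of the injection".
- **Section 9.4.5 (Evaluation of Safety)** restricts collection: "As this is a non-interventional study, only treatment-related Adverse Events (AEs) will be recorded". It then plans a tabulation of treatment-related emergent events (TRAEs) and of all reported SAEs, with further "tabulated summaries according to maximum severity, relationship with the drug". The definition begins: "TRAE is defined as any AE occurring during the active phase of the study". One of three limbs must also be met: the event is new since the first dose; or it was present before and became more severe; or it was present before at the same severity and its link to the drug was established later.
- **Section 11.2** opens with: "Every adverse reaction, independently of its severity and of its suspected relationship with the study drug, should be recorded".
- **Section 11.2.1** defines an adverse reaction as a harmful response to a drug and has the investigator evaluate every adverse event. The specific form is to be used where "there were or there could be a causal relationship with the study drug". The items on that form include "causality assessment: related, unrelated".

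**The concern.** The scope of adverse-event collection has to be fixed before the first patient enters. The separate analysis plan announced in section 8.4 (Statistical/Analytical Methods) can choose what to tabulate, but it cannot recover an event that nobody wrote down. If investigators read the rule differently, the pooled incidence figures would mix two kinds of numerator, all events from some sites and related events from others. The study is planned at some 60 centres, so differing readings are possible.

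Adverse events are not among the objectives in section 5. Section 9 (Ethical Aspects) does, however, expect the study to yield information on drug safety in routine practice, so the safety tables have a stated purpose.

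**Working it through.** No plan figure is to be reproduced and no arithmetic applies. The check is to set the rules side by side.

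**Step 1: is there a direct conflict?** Take an event that the investigator judges unrelated to the LHRH analogue. Section 8.3 requires it to be recorded. Section 9.4.5 says that only treatment-related events are, so it is not. Both are current text and neither refers to the other. The conflict is direct.

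**Step 2: do the visit lists decide it?** Sections 8.4.1 and 8.4.2 name events considered associated with the LHRH analogues. That supports the narrow reading. But each is a list of items to collect and neither says that other events are left out. A site recording every event with its causality would satisfy 8.3, 8.4.1 and 8.4.2 and depart only from 9.4.5.

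**Step 3: does section 11.2 decide it?** Its opening sentence uses a causal term (adverse reaction) but waives the causal judgement; taken literally it leans wide. Section 11.2.1 sends to the specific form only events with an actual or possible causal link, which leans narrow, and then offers *unrelated* as a value on that form. It leaves the scope open.

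**Step 4: what happens in the planned tables?** Follow several kinds of event through both rules.

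| Event | Recorded under 8.3 | Recorded under 9.4.5 | A TRAE by the 9.4.5 definition, if recorded |
|---|---|---|---|
| Related, new after first dose | yes | yes | yes (first limb) |
| Unrelated, new after first dose | yes | no | yes (first limb) |
| Unrelated, present before, worse later | yes | no | yes (second limb) |
| Unrelated, present before, same severity | yes | no | no |

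Two of the three limbs test only timing or severity. Write R for the number of related TRAEs and U for the number of unrelated events that are new or worsened. The TRAE count is R under the narrow rule and R + U under the wide one. The Protocol gives no adverse-event rates, so U is unknown and the difference cannot be sized. The summary by relationship with the drug is affected the other way: it is informative under the wide rule and has little content if only related events were recorded.

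**Step 5: are serious events protected?** The restriction in 9.4.5 makes no exception for serious events. The expedited routes in 11.2, 11.2.2 and 11.2.3 cover severe adverse reactions, and 11.2.1 defines a reaction by its causal link to a drug. Under the narrow rule an unrelated serious event therefore has no clear recording route, while 8.3 would capture it. The scope of the SAE table in 9.4.5 is then undefined.

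**The case against.** The strongest reply is that the conflict is one of wording with little consequence. One CRF, specifically designed for the study, serves all sites. It is not shown, and it may ask a single clear question that every site answers alike. Adverse events are not a listed objective, there is no control group and no test of adverse-event rates is planned. This stands, and it sets the priority. It does not remove the contradiction, because the CRF has to implement one of two incompatible sentences.

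Three stronger readings are tempting, and the Protocol does not support them.

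- *The visit lists forbid recording unrelated events.* They do not say so. The only express restriction is in 9.4.5.
- *The TRAE definition is a second, independent error.* Within 9.4.5 alone, the events have already been limited to related ones, and timing limbs applied to those do yield treatment-related emergent events. The definition misfires only if 8.3 governs, so it is mainly a consequence of the same conflict.
- *Sites will have collected different data.* That is possible, but it cannot be shown without the CRF.

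Section 11.2.1 can also be read as limiting one form rather than all recording in the CRF. That is fair, and it is a reason to call the section unsettled rather than contradictory.

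It would be too reassuring, on the other hand, to assume that serious events escape the problem. Nothing in 9.4.5 exempts them, and the reporting sections speak of reactions.

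**Conclusion.** The point holds. Sections 8.3 and 9.4.5 give incompatible recording rules, and neither the visit lists nor section 11.2 resolves them. The TRAE count, the relationship summary and the scope of the SAE table all depend on which rule is followed.

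Confidence in the textual conflict is high. Confidence in any effect on the data is limited, because the CRF is unseen and no event rates are given. The metabolic-syndrome endpoint, its confidence interval and the sample size are unaffected. Priority is minor, but the correction is cheap and has to come before data collection.

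**What to change.** State one recording rule, word it alike in 8.3 (Adverse Event Recording), 8.4.1, 8.4.2, 9.4.5 and 11.2, and check that the CRF asks the same question.

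- **If the narrow rule is kept** (fewest edits): amend 8.3 and the opening sentence of 11.2. Remove or redefine the *unrelated* option in 11.2.1 and the relationship summary in 9.4.5. State explicitly whether serious events are recorded regardless of causality, so that the SAE table has a defined scope.
- **If the wide rule is kept**: amend 9.4.5 and the two visit lists. Either add a causal condition to the TRAE definition or rename the category treatment-emergent.

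The cost is wording in five sections and a CRF check. The narrow rule leaves unrelated events uncollected, including serious ones unless an exception is written in. The wide rule adds recording work at three visits (baseline, Month 6 and Month 12).
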